7.1 DEMOGRAPHIC AND OTHER BASELINE CHARACTERISTICS

Only descriptive statistics are planned for this section of the report.

7.1.1 Disposition of patients

For patient disposition the standard descriptive table from the EOT catalogue will be populated. Additionally, patients with discontinuations by initial treatment and the reasons will be listed and tabulated, overall and for each treatment separately. The same output will also contain an overview of discontinued and non-discontinued, as well as completed and non-completed patients.

7.1.2 Important protocol violations

A table and a listing of patients with important protocol violations based on [Table 6.2: 1](#) will be created in Section 15.1.3 and Appendices 16.2.3 and 16.1.9.2.3 (if needed) respectively, of the CTR.

7.1.3 Demographic and other baseline characteristics

Standard descriptive analysis and summary tables for all patients treated by initial treatment will be created for demographic data, oncological history and baseline conditions.

7.2 CONCOMITANT DISEASES AND MEDICATION

Only descriptive statistics are planned for this section of the report. Concomitant diseases will be coded similarly as adverse events based on the most current Medical Dictionary for Regulatory Activities (MedDRA) version. Concomitant therapies will be coded according to World Health Organisation - Drug Dictionary (WHO-DD). Concomitant therapies (CT) will be classified according to the Anatomical, Therapeutic, Chemical (ATC) classification system. The third ATC level will be used to categorise CTs by therapy type. In situations where a medical product may be used for more than one equally important indication, there are often several classification alternatives. As appropriate, patients receiving CTs with more than one possible ATC level-three category will be counted more than once; footnotes will clarify this possible double counting in tables.

Concomitant medications will be presented according to whether they are concomitant with the reception of study medication, or whether they were given prior to study medication. In case start and stop dates of the medications are completely missing, they are assigned as given prior to study medication.

Proprietary confidential information © 2017 Boehringer Ingelheim International GmbH or one or more of its affiliated companies

7.3 TREATMENT COMPLIANCE

Compliance was not analysed separately, but assessed in terms of exposure (including dose intensity). Refer to [Section 7.7](#) for further details on exposure analysis.

7.4 PRIMARY ENDPOINTS

7.4.1 First part

The primary endpoints are the MTD and the occurrence of DLT. The MTD is determined from the occurrences of DLTs during the MTD evaluation period (this period is defined in [Section 5.1.1](#)). An overall summary of the DLTs (see CTP Section 5.2.6 for definitions of DLT) which occurred during the MTD evaluation period and the on-treatment period will be provided for each dose cohort.

Patients that were treated but replaced for the MTD evaluation (see CTP Section 3.3.4.3) will be excluded from the MTD determination. Replacement of patients will be determined on a case by case basis; exclusion of these patients from the MTD evaluation will be confirmed by the trial team at the report planning meeting prior to database lock.

A listing of patients with DLTs by initial treatment will be performed.

At the end of the dose escalation phase, a safety analysis will be performed to determine the RP2D. The results will be documented for internal use and communication with the participating investigators. (see also in [Section 9.1](#))

7.4.2 Second part

Objective response (OR)

OR as assessed by investigators is defined as a best overall response of CR or PR and will be analysed. Descriptive statistics including number of treated patients, number of patients with objective response as best overall response and the corresponding percentages will be presented and evaluated.

The same analysis will also be done for RP2D patients (defined as pooled patients of all the patients in part B and the patients starting with xentuzumab 1000mg + afatinib 40mg in part A excluding squamous carcinoma patients).

7.5 SECONDARY ENDPOINTS

7.5.1 Key secondary endpoints

This section is not applicable as no key secondary endpoint has been specified in the protocol.

7.5.2 Other secondary endpoints

7.5.2.1 First part

This section is not applicable as no secondary endpoint has been specified in the protocol.

Proprietary confidential information © 2017 Boehringer Ingelheim International GmbH or one or more of its affiliated companies

7.5.2.2 Second part

Disease control

Disease control (DC) is defined as best overall response of complete response (CR) or partial response (PR) or stable disease (SD) (defined in [Section 5.2.2.2](#)). Only descriptive statistics are planned for this section of the report.

Time to OR

For patients with objective response, time to objective response will be shown on patient level. If applicable a set of summary statistics for time to objective response on cohort level will also be produced.

Duration of OR

For patients with objective response, duration of objective response will be shown on patient level. If applicable a set of summary statistics for duration of objective response on cohort level will also be produced.

The same analysis will also be done for RP2D patients (defined as pooled patients of all the patients in part B and the patients starting with xentuzumab 1000mg + afatinib 40mg in part A excluding squamous carcinoma patients).

7.7 EXTENT OF EXPOSURE

The variables defined in [Section 5.4.2](#) will be summarised descriptively for each dose cohort.

Proprietary confidential information © 2017 Boehringer Ingelheim International GmbH or one or more of its affiliated companies

7.8 SAFETY ANALYSES

All safety analyses will be performed on the TS (unless otherwise specified; for example, the MTD Set will be used for some safety outputs). Patients in the first part of the trial who were replaced within or before the first treatment cycle will be excluded from the determination of the MTD.

7.8.1 Adverse events

The analyses of AEs will be descriptive in nature. All analyses will be based on the number of patients with AEs (not the number of AEs).

For analysis multiple AE occurrence data on the CRF will be collapsed into an AE event provided that all of the following applies:

- All AE attributes are identical (Lowest Level Term (LLT), Common Terminology Criteria for Adverse Events (CTCAE) grade, action taken with trial medication, therapy required, seriousness, reason for seriousness, relationship, outcome, AE of special interest)
- The occurrences were time-overlapping or time-adjacent (time-adjacency of 2 occurrences is given if the second occurrence started on the same day or on the day after the end of the first occurrence)

For further details on summarisation of AE data, please refer to (2) and (4).

Adverse events will be coded with the most recent version of MedDRA. The severity of AEs will be scaled according to CTCAE (CTCAE version 4.03 (10)).

The analyses of adverse events will be based on the concept of treatment-emergent adverse events. That means that all adverse events with an onset between first treatment administration until end of the REP will be assigned as 'on treatment'. All adverse events occurring before first drug intake will be assigned to 'screening' and all adverse events occurring after the residual effect period will be assigned to 'post-treatment'; these AEs will be displayed in listings only. Adverse events will be displayed by the initial dose of study medication administered on the first day of treatment .

An overall summary of adverse events will be presented. The frequency of patients with adverse events will be summarised by treatment, primary system organ class and preferred term.

Separate tables will be provided for patients with drug-related adverse events, adverse events leading to dose reduction, adverse events leading to discontinuation, serious adverse events, serious drug-related serious adverse events, adverse events leading to death, other significant adverse events, adverse events of special interest, and adverse events fulfilling the DLT definition (for part A only), and drug-related adverse events leading to discontinuation.

Sorting order:

In tables presenting System Organ Classes (SOCs) and Preferred Terms (PTs), SOCs will be sorted alphabetically and PTs (within SOC) by descending frequency.

Reporting of CTCAE grades in tables:

Proprietary confidential information © 2017 Boehringer Ingelheim International GmbH or one or more of its affiliated companies

In tables showing AEs by worst CTCAE grade, AEs with missing CTCAE grade will only be displayed under the category "All grades", but no category "Missing grade" will be displayed. Therefore the categories "Grade 1" to "Grade 5" might not add up to the category "All grades"; a footnote will explain this handling.

Displaying of CTCAE grades in AE tables (Section 15) will be "All grades", "Grade 1", "Grade 2", "Grade 3", "Grade 4", and "Grade 5" separately.

Listings of adverse events

Adverse events will be reported with start and end day as calculated from the first day of treatment with study medication.

Incidence and severity of adverse events

The incidence of AEs overall (irrespective of relatedness to study medication), related AEs, and serious AEs (SAE) will be reported by severity according to CTCAE grades.

Other significant adverse events

Other significant AEs are defined as serious and non-serious AEs that lead to dose reduction or permanent discontinuation of study medication. Their incidence will be reported by severity according to CTCAE grades.

A listing of patients who developed 'other significant' AEs will be provided and a flag for serious and non-serious will be included.

AEs leading to dose reduction or permanent discontinuation will include:

- AEs leading to dose reduction of xentuzumab
- AEs leading to dose reduction of afatinib
- AEs leading to permanent discontinuation of xentuzumab
- AEs leading to permanent discontinuation of afatinib

AEs leading to death

AEs leading to death during the on-treatment period will be tabulated in a separate table. In this table no CTCAE grades will be shown. For fatal AEs without CTCAE grade 5 or missing grade, the grade will be imputed as CTCAE grade 5. Reported fatal AEs that occurred in the follow-up period will be listed.

Protocol-specified Adverse Events of Special Interest (AESI)

Protocol-specified AESIs are specified in the CTP Section 5.2.2.1. Their incidence will also be reported.

Adverse events by user defined AE categories (UDAEC)

User defined adverse events categories (UDAEC) as defined on project level by the pharmacovigilance working group will be derived and the latest version will be used for the analysis. The most recent version of the categories is defined in a document entitled "8-02-sap-safety-core", which can be found in the Project Data Management and Statistics folder, section 8 (project level), within BIRDS. The incidence of AE by UDAEC will be analysed.

Proprietary confidential information © 2017 Boehringer Ingelheim International GmbH or one or more of its affiliated companies

7.8.2 Laboratory data

7.8.2.1 Laboratory data

The analyses of laboratory data will be descriptive in nature and will be based on BI standards (5). The same on-treatment periods as considered for the analysis of adverse events will be applied for laboratory values except for that the baseline laboratory value will be included in the 'on-treatment' period. Patients having at least one post-baseline laboratory value will be displayed in the descriptive analyses.

Descriptive statistics, including change from baseline and frequency of patients with transitions relative to the reference range, will be provided. CTCAE grades for applicable laboratory parameters will be calculated according to CTCAE version 4.03 (10). The following outputs will be presented:

- Worst CTCAE grade experienced during the on-treatment phase.
- Transitions of CTCAE grade from baseline to worst laboratory value, from worst to last laboratory value during the on-treatment phase, and from baseline to last laboratory value.

Patients with missing CTCAE grade at baseline or no baseline value but post baseline values will be displayed in the category "Missing CTCAE grade at baseline". Laboratory values without CTCAE grading will be compared to their reference ranges and frequency tables will be provided for the number of patients within and outside the reference range at baseline and the last measurement on treatment.

Analysis of potentially clinically significant abnormal laboratory values, and handling of CTCAE grade -1 and -9 laboratory parameters, are described in the SOP for "Display and analysis of laboratory data" (5), Reference Document 9.

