6 GENERAL ANALYSIS DEFINITIONS

6.1 TREATMENTS

Part A and part B: Patients will be analysed according to the cohort initially assigned. All planned analysis will be presented by this cohort, unless specified otherwise. Handling of patients where cohort assignment has not been followed will be handled on a case-by-case basis, to be agreed at report planning meetings or DBL meeting (but prior to database lock).

For safety summaries data recorded during the Residual Effect Period (REP) will be considered as on-treatment. For this trial, the length of the REP is 42 days.

The actual study periods and treatment codes are defined in a document entitled “8-07-other-sdtm-trial-arms-trial-elements”, which can be found in Data Management and Statistics (DMS) folder, Section 8, within BIRDS.

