6.7 BASELINE, TIME WINDOWS, AND CALCULATED VISITS

6.7.1 Baseline

The last measurement observed prior to start of trial medication will be assigned to baseline. Note that for some trial procedures (for example body weight, vital signs, laboratory tests) this may be the value measured on the same day trial medication was started. In these cases it will be assumed that the measurements were taken prior to the intake of any study medication. For tumour assessment, baseline evaluations must be based on Magnetic Resonance Imaging (MRI) or Computed Tomography scans performed no more than 30 days prior to start of trial medication.

Study days and visits will be labelled according to the flow chart of the CTP.

Unless otherwise specified, baseline is defined as the latest time-point before the very first administration of any study medication. If this criterion is not fulfilled then no baseline will be derived.

Laboratory values:

Baseline is defined as the latest time-point before the very first administration of any study medication.

If any of these times are missing and the date of laboratory value is equal to the date of first study drug administration, then the laboratory assessment will be considered as according to protocol, i.e. as prior to first study medication.

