7.8.2.2 Laboratory values of special interest

Hepatic enzyme elevations (potential Hy's law cases):

These are defined as those cases where a combination of all of the following events occurred: any on-treatment value of ALT and/or AST $> 3\text{ULN}$ with total bilirubin $\geq 2\text{ULN}$ and ALKP $< 2\text{ULN}$. The events can occur in any order, but must occur within 14 days of the previous event, i.e. the second event must occur within 14 days of the first event, and the third event must occur within 14 days of the second event, etc.

Patients with missing laboratory values for liver enzymes will be excluded from these analyses but will be presented separately in a listing. Tabulations of hepatic enzyme elevations and liver laboratory values (see Section 5.2.2.1 of the CTP), including flags of true DILI cases, are created in accordance with the Food and Drug Administration (FDA) DILI guidance (8).

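### The SAP puts the pre-dose laboratory baseline inside the on-treatment period, so the worst-grade table and the worst-to-last transition can report a pre-treatment abnormality as an on-treatment one

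*SAP*

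**What the plan says.** SAP section 7.8.2.1 applies the adverse-event on-treatment period to laboratory values, "except for that the baseline laboratory value will be included in the" on-treatment period. Section 6.7.1 fixes what that value is: "baseline is defined as the latest time-point before the very first administration of any study medication".

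The period being borrowed is in section 7.8.1, where "all adverse events with an onset between first treatment administration until end of the REP will be assigned as 'on treatment". Adverse events before first intake go to screening and appear only in listings. On the length of the residual effect period, section 6.1 says "For this trial, the length of the REP is 42 days". Protocol section 7.3.3 also starts the on-treatment period at first administration and presents earlier events separately.

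Section 7.8.2.1 then lists the outputs. One is "Worst CTCAE grade experienced during the on-treatment phase". Another begins "Transitions of CTCAE grade from baseline to worst laboratory value" and goes on to worst-to-last and baseline-to-last. Change from baseline is also summarised. A patient needs a post-baseline value to be displayed. That decides which patients appear, not which of their values may count as the worst.

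Section 7.8.2.2 builds the potential Hy's law screen on "any on-treatment value of ALT and/or AST" above 3 times ULN, together with bilirubin and alkaline phosphatase conditions linked by 14-day gaps.

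**The concern.** The trial has no control group (Protocol section 3.2), so no comparator arm shows how much laboratory abnormality patients brought with them. Safety of the combination is the secondary objective of both parts. Abnormal baselines are to be expected. Inclusion criterion 12 allows AST/ALT up to 3 times ULN (5 times if related to liver metastases) and bilirubin up to 1.5 times ULN, and it sets no haemoglobin limit. Protocol section 5.2.2.1 has a separate liver rule for patients whose transaminases are raised at baseline.

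A stand-alone worst-grade table has no baseline column. If the pre-dose value may be the worst value, a reader of that table cannot separate abnormality present before treatment from abnormality that arose on it. Adverse events with pre-dose onset are kept out of the on-treatment tables, so the two halves of the safety section would follow opposite rules.

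**Working it through.** There is no stated figure in the plan to reproduce here. The check is what the rule does to each output.

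**Set-up.** Let b be the baseline grade and m the worst post-dose grade, each from 0 to 4, giving 5 × 5 = 25 pairs. With baseline included, as the SAP reads, worst = max(b, m). With baseline excluded, worst = m. The two differ only when b > m, which is 4 + 3 + 2 + 1 = 10 pairs.

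| Quantity | Baseline included | Baseline excluded |
|---|---|---|
| Pairs where the worst grade differs between rules | 10 of 25 (all higher when included) | – |
| Pairs where the worsening classification (worst > b) differs between rules | 0 of 25 | – |
| Pairs that can show improvement (worst < b) | 0 of 25 | 10 of 25 |

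These are counts of possible grade pairs, not of patients.

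**Output by output.**
- Worst on-treatment grade: affected. A patient with b > m is reported at b.
- Baseline to worst: a carried baseline grade lies on the diagonal as no change. Worsening cells are the same under both rules; improvement cells are empty by construction.
- Worst to last: affected. Take baseline Grade 2, worst post-dose Grade 1, last Grade 0. The SAP rule shows 2 to 0, as if recovering from an on-treatment Grade 2. Post-dose values alone show 1 to 0.
- Baseline to last, and change from baseline: unaffected.

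**Potential Hy's law screen.** Entry AST/ALT above 3 times ULN is allowed only with liver metastases, and entry bilirubin is capped at 1.5 times ULN against a screen threshold of 2 times. For an eligible patient, baseline could therefore supply the transaminase component in that subgroup, while bilirubin would normally have to rise afterwards and within 14 days. Course 1 safety laboratory tests on Days 8 and 15 are 7 and 14 days after a Day 1 baseline, so the route exists but is narrow.

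**Scale, on assumed rates only.** Let q be the share of patients with baseline Grade 1 or higher in a given parameter, and r the share of those whose post-dose values are all Grade 0. The any-grade count is then too high by q × r. The documents give neither rate. With q from 10% to 30% and r from 25% to 50%, the excess runs from 0.10 × 0.25 = 2.5 to 0.30 × 0.50 = 15 percentage points, or 18 × 0.025 = 0.45 to 18 × 0.15 = 2.7 of the 18 Part B patients. With r = 0 it is zero.

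**The case against.** The strongest reply is that section 7.8.2.1 rests on an internal laboratory standard (SAP reference 5) that is not among the documents. That standard may limit the worst value to post-baseline measurements. On this view the baseline clause only keeps baseline in by-visit and transition displays, and the SAP nowhere says outright that the worst value may be the baseline one. This is possible and cannot be checked. It does not settle the matter: the SAP's own sentence places baseline in the period over which the worst grade is taken, and nothing else in the SAP takes it out. If the standard does restrict it, the SAP should say so.

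Other parts of the reply stand. A reader might infer that the baseline-to-worst tables present pre-treatment abnormality as toxicity. They do not, since carried grades show as no change. A reader might also infer that improvement is hidden altogether. It is lost from one table but remains partly visible in baseline-to-last and change from baseline.

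The number affected may be small. The worst-grade entry changes only if every post-dose value is better than baseline, and tests are weekly in Course 1 and twice per course afterwards. Inclusion criterion 13 limits residual toxicity from prior therapy to Grade 1, with two exceptions that are not laboratory findings. Clinically relevant laboratory changes are also recorded as adverse events, and those tables exclude pre-dose onset.

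**Conclusion.** The point holds for two outputs as written: the stand-alone worst-grade table and the worst-to-last transition. In the baseline-to-worst table the only loss is the improvement cells. For the Hy's law screen it is an edge case, and that screen only identifies potential cases.

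The direction is certain under the literal reading: including baseline can raise a reported worst grade but never lower it. The size is not established. The 2.5 to 15 point range above depends wholly on assumed rates.

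It would be tempting to carry this over to dose selection, but the documents do not support that. MTD rests on first-course DLTs. The Part A safety analysis in SAP section 9.1 lists transitions from baseline to worst grade, where worsening counts are unchanged, and does not list the stand-alone worst-grade table. Efficacy is untouched. This is a correction worth making to descriptive safety tables in an uncontrolled trial; it does not undermine the trial's main conclusions.

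**What to change.** In SAP section 7.8.2.1, state that the worst grade or worst value is derived only from measurements taken after first administration and up to the end of the 42-day residual effect period. Baseline should serve only as the reference in transition and change-from-baseline displays. Apply the same limit to the worst-to-last transition and to the on-treatment values used in the section 7.8.2.2 screen. If the internal standard already does this, cite the rule explicitly and remove the conflicting clause.

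If a baseline-inclusive table is wanted for another reason, label it that way and add a count of patients whose grade worsened from baseline.

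The cost is one sentence, a post-baseline derivation flag, and a rerun of any affected tables already produced. No new data are needed.
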